6.2. Statistical Tests

Unless otherwise specified, all formal statistical tests of treatment effects will be done at two-sided significance level of 0.05. Point estimates will be accompanied with two-sided 95% CIs where applicable.

6.3. Data Review Meeting

Prior to database lock, a data review meeting (DRM) was conducted at November 26, 2019. Protocol deviation and handing of subjects and records, for analysis sets and evaluations, was confirmed during DRM.

No protocol deviation was observed during the study. As a results of DRM, all subject was included in SAF and PK analysis set.

The PK data handling was assessed during DRM. All PK data were considered valid and included in the calculation of PK parameters and in the summary tables and figures.

7. DATA CONVENTIONS

7.1. Analysis Variable Definitions

7.1.1. Study Subjects

7.1.1.1. Demographic and Other Baseline Characteristics

(1) BMI

BMI will be recalculated using the formula below and reported to 1DP.

BMI (kg/m²) = weight at Day -1 (kg) / {height at screening (m)}²

(2) Age at informed consent

Age (year) = year of informed consent – year of birth

Subtract 1 from the age (years) calculated above, if [Month of informed consent < Month of birth] or [Month of informed consent = Month of birth AND Day of informed consent < Day of birth].

7.1.1.2. Medical History

Medical history will be coded according to the MedDRA version 22.0.

7.1.1.3. Prior or Concomitant Medication

Medications will be coded according to the WHO Drug Global B3 Format March 1, 2019.

(1) Prior Medication

Prior medication is any medication that was stopped prior to the investigational product administration.

(2) Concomitant Medication

The investigator (or subinvestigator) will confirm whether each subject has used any medications (including commercially available drugs) other than the investigational product, between the start of investigational product administration and completion of the end-of-study assessment.

7.1.2. Safety Assessments

7.1.2.1. Adverse Events

Adverse events will be coded according to the MedDRA version 22.0

(1) Adverse Events/ Serious Adverse Events (AEs/SAEs)

An AE/SAE is any untoward medical occurrence or unintended sign (including an abnormal laboratory finding), symptoms, and disease in a patient or subject who is administered a pharmaceutical product during safety assessment period, and which does not necessarily need to have a causal relationship with the treatment.

(2) Adverse Drug Reaction

A AE is considered “adverse drug reaction” if it has been assessed as having a “reasonable possibility” in relationship to the investigational product .

(3) Time to Adverse Events

Time to Adverse Events occurrence (days) = AE start date – date of first administration + 1

(4) Duration of Adverse Events

Duration of Adverse Events (days) = AE stop date – AE start date + 1

(5) Period of Adverse Events

Visit in Group 1	Visit in Group 2	Visit in Group 3	Visit in Group 4	For TFLs
From on or after administration date/time in Day 1 to before administration date/time on in day 3	From on or after administration date/time in Day 7 to before administration date/time on in day 23	From on or after administration date/time in Day 5 to before administration date/time on in day 7	From on or after administration date/time in Day 3 to before administration date/time on in day 5	Fasted
From on or after administration date/time in Day 3 to before administration date/time on in day 5	From on or after administration date/time in Day 1 to before administration date/time on in day 3	From on or after administration date/time in Day 7 to before administration date/time on in day 23	From on or after administration date/time in Day 5 to before administration date/time on in day 7	8 hours after high-fat meal
From on or after administration date/time in Day 5 to before administration date/time on in day 7	From on or after administration date/time in Day 3 to before administration date/time on in day 5	From on or after administration date/time in Day 1 to before administration date/time on in day 3	From on or after administration date/time in Day 7 to before administration date/time on in day 23	4 hours after low-fat meal
From on or after administration date/time in Day 7 to before administration date/time on in day 23	From on or after administration date/time in Day 5 to before administration date/time on in day 7	From on or after administration date/time in Day 3 to before administration date/time on in day 5	From on or after administration date/time in Day 1 to before administration date/time on in day 3	2 hours after light meal
From on or after administration date/time in Day 23 to end of study assessment	From on or after administration date/time in Day 23 to end of study assessment	From on or after administration date/time in Day 23 to end of study assessment	From on or after administration date/time in Day 23 to end of study assessment	2 hours after low-fat meal

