5.2.2 Study Period and Evaluation Period

Study period:

The study period is defined as the period from the time of obtaining the informed consent to the time of completion of the end-of-study assessment or discontinuation assessment (for subjects who have entered into the follow-up period, to the time of completion or termination of the follow-up).

Screening:

Subjects providing informed consent will be screened for eligibility to select subjects meeting all of the inclusion criteria and none of the exclusion criteria (16 subjects with a few reserve subjects).

Confidential

Evaluation period: The evaluation period is defined as the period from completion of dosing of the investigational product on Day 1 to completion of the end-of-study assessment or discontinuation assessment. The duration of hospitalization will be 10 days and 9 nights (Day -1 to Day 9) for Period I to Period IV, and 4 days and 3 nights (Day X to Day X+3) for Period V.

End-of-study assessment: The prespecified observations and tests will be performed as the end-of-study assessment, 7 days (± 2 days) after the last dose of the investigational product.

[Rationales for setting]

A crossover design was selected for this study in order for PK parameters to be precisely compared in a small number of subjects in accordance with the "Partial Revision of Guidelines including the Guideline for Bioequivalence Studies of Generic Products" (PFSB/ELD Notification No. 0229-10 dated February 29, 2012) [1] and the Guidance for Industry: Bioavailability and Bioequivalence Studies Submitted in NDAs or INDs - General Considerations (March 2014) [2].

The duration from discharge in period IV to admission in period V was set to 11-18 days as the duration necessary to obtain PK results from period I to IV.

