3.2.2. Study Period and Evaluation Period

Study period: The study period is defined as the period from the time of obtaining the informed consent to the time of completion of the end-of-study assessment or discontinuation assessment (for subjects who have entered into the follow-up period, to the time of completion or termination of the follow-up).

Screening: Subjects providing informed consent will be screened for eligibility to select subjects meeting all of the inclusion criteria and none of the exclusion criteria (16 subjects with a few reserve subjects).

Evaluation period: The evaluation period is defined as the period from completion of dosing of the investigational product on Day 1 to completion of the end-of-study assessment or discontinuation assessment. The duration of hospitalization will be 10 days and 9 nights

(Day -1 to Day 9) for Period I to Period IV, and 4 days and 3 nights (Day X to Day X+3) for Period V.

End-of-study assessment: The prespecified observations and tests will be performed as the end-of-study assessment, 7 days (± 2 days) after the last dose of the investigational product.

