3.4. Sample Size and Power Considerations

Total of 16 subjects (4 subjects per group)

[Rationales for setting]

The target number of subjects was set on the assumption that it would allow obtaining results that will meet the study objectives although it is not based on statistical calculations.

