8.3.1. Adverse Events

Overall summary for the following will be conducted by treatment.

- Subjects with at least one AE
- Subjects with at least one adverse drug reaction
- Subjects with at least one SAE
- Subjects with at least one serious adverse drug reaction
- Subjects with at least one AE leading to discontinuation of investigational product
- Subjects with AE leading to death

The following summaries also will be conducted by treatment.

- AEs by SOC and PT
- Adverse drug reactions by SOC and PT
- AEs by SOC, PT and severity

Each of the summaries will be done at the subject level - multiple occurrences of the same event within a subject will be counted once in the summaries by SOC and PT; multiple occurrences of the same event within a subject will be counted once in the maximum severity category (severe > moderate > mild) and/or maximum drug relationship category (reasonable possibility/no reasonable possibility) and/or the earliest duration.

All AEs will be listed.

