9.3. Analysis Visits to Report

(1) Non-PK related

Analysis Visit	Analysis Time Point	Apply to	Laboratory Tests	Vital Signs	12-Lead ECGs
Screening		X		X	X
Day -1		X (baseline)		X	X
Day 1	Pre-dose			X (baseline)	X (baseline)
Day 1	1 hour			X	X
Day 2	24 hours			X	X
Day 3	Pre-dose			X (baseline)	X (baseline)
Day 3	1 hour			X	X
Day 4	24 hours			X	X
Day 5	Pre-dose	X		X (baseline)	X (baseline)
Day 5	1 hour			X	X
Day 6	24 hours			X	X
Day 7	Pre-dose			X (baseline)	X (baseline)
Day 7	1 hour			X	X
Day 8	24 hours			X	X
Day 9	46 hours	X		X	X
Day 23		X		X	X
Day 24	Pre-dose			X (baseline)	X (baseline)
Day 24	1 hour			X	X
Day 25	24 hours			X	X
Day 26	48 hours	X		X	X
Follow up		X		X	X

Screening, unscheduled visits, retests (same visit number assigned) will not be displayed in by-visit summary tables, but will be included in the data listings.

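### Adverse-event windows of about 2, 16–17 and 5–9 days make Period V non-comparable with conditions A–D and add between-group noise within A–D

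*SAP*

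**What the plan says.** The table in SAP 7.1.2.1(5) defines when an adverse event belongs to a condition. The window opens at that condition's dose and closes at the next dose.

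- Period I: "From on or after administration date/time in Day 1 to before administration date/time on in day 3". Periods II and III follow the same two-day pattern.
- Period IV: "From on or after administration date/time in Day 7 to before administration date/time on in day 23".
- Period V, all groups: "From on or after administration date/time in Day 23 to end of study assessment". SAP 3.2.2 puts that assessment "7 days (± 2 days) after the last dose of the investigational product".

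SAP 8.3.1 then states: "Overall summary for the following will be conducted by treatment". The tables by system organ class and preferred term are also by treatment. Protocol 13.4.3 asks for the number and proportion of subjects by dosing condition. SAP 6.1 takes the number of subjects in the treatment group as denominator. Neither document adjusts for time at risk or sets a fixed post-dose window. The SAP's time-to-event variable counts from the first dose of the study, so it does not give time since the condition's own dose.

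The Period V dose day differs within the SAP. Section 7.1.2.1(5) uses an administration on Day 23. Section 9.3 has no pre-dose row on that day; it lists "Day 24 Pre-dose" and the 1-hour assessment also on Day 24.

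**The concern.** A percentage of subjects with an event depends on how long each subject is watched. Here, subjects in the same column are watched for very different times. For each of A–D, twelve subjects contribute about 2 days and four contribute 16–17 days. Which four changes with the condition: Group 2 for fasted, Group 3 for high-fat, Group 4 for low-fat at 4 hours, Group 1 for the light meal. Most of the long window is spent at home, where the inpatient limits on alcohol, nicotine and caffeine no longer apply until 24 hours before readmission (Protocol 8.5.1).

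The Period V column has a third length, the same for all 16 subjects. A reader who sets the five columns side by side would take a difference in observation time for a difference between meals. An event ten days after a single dose says little about the meal: the suspension's terminal half-life is 5.1–11.8 hours (Protocol section 1), so 48 hours already spans about 4 to 9 half-lives.

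**Working it through.** The plan states no event rate or exposure figure to reproduce, so the check starts from the windows.

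**Inputs.** Sixteen subjects, four per sequence group (SAP 3.4). In the 4×4 square, each of A–D falls once in each of Periods I–IV (SAP 3.2.1). Windows in days: Periods I–III, 2; Period IV, L = 16 (Day 7 to Day 23) or 17 (Day 7 to Day 24); Period V, 7, range 5–9.

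**Subject-days for each of A–D:** 4 × (2 + 2 + 2 + L).

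- L = 16: 4 × 22 = 88, of which the Period IV group has 64/88 = 73%.
- L = 17: 4 × 23 = 92, of which the Period IV group has 68/92 = 74%.
- Discharge is on Day 9 and the next visit on Day 23 (SAP 9.3), so about 14 days of the Period IV window are at home: 4 × 14/88 = 64%, or 4 × 14/92 = 61%, of the condition's total.
- Protocol 5.2.2 says "The duration from discharge in period IV to admission in period V was set to 11-18 days". That planned range gives L = 14 to 21 and a Period IV share of 70–78%.

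**Subject-days for Period V:** 16 × 7 = 112 (16 × 5 = 80 to 16 × 9 = 144). The ratio to A–D is 112/92 = 1.22 to 112/88 = 1.27.

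**Expected proportion with at least one event.** Assume a constant background rate r per subject-day and no effect of meal or dose. The documents give no such rate, so a range is shown.

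- A–D: [3(1 − e^(−2r)) + (1 − e^(−Lr))]/4
- Period V: 1 − e^(−7r)

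| r per day | A–D, L = 16 / 17 | Period V, 7 days | Ratio, L = 16 / 17 | Share of A–D count from Period IV group, L = 16 / 17 |
|---|---|---|---|---|
| 0.005 | 2.7% / 2.8% | 3.4% | 1.29 / 1.24 | 72% / 73% |
| 0.01 | 5.2% / 5.4% | 6.8% | 1.30 / 1.25 | 71% / 72% |
| 0.02 | 9.8% / 10.1% | 13.1% | 1.33 / 1.29 | 70% / 71% |
| 0.04 | 17.6% / 18.1% | 24.4% | 1.39 / 1.35 | 67% / 68% |

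With the end-of-study visit anywhere from day 5 to day 9, the ratio runs from 0.89 to 1.72. At 7 days, the excess in Period V is about 0.1 to 1.1 subjects of 16. A, B, C and D have identical expected proportions in every row.

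**When do late events dominate a column?** Let each dose add an expected d events within 48 hours. With L = 16, an A–D condition expects 16d + 88r events, of which 4 × 14 × r = 56r fall after 48 hours. That is more than half only if 56r > 8d + 44r, that is d < 1.5r. With L = 17 the limit is 60r > 8d + 46r, or d < 1.75r. The documents give neither d nor r.

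**With a window ending at the 46/48-hour assessment:** 16 × 2 = 32 subject-days per condition, or 16 × 46/24 = 30.7 where that assessment is at 46 hours. For a 2-day window the expected background proportion is 1.0% to 7.7% over the same rates, the same in all five columns apart from those two hours.

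**The case against.** The strongest reply is that the crossover already protects the comparison that matters. All four conditions have the same mix of window lengths, so length cannot favour one of A–D. That stands. A reader might infer that the by-condition rates are biased within A–D, or that they mostly reflect window length. The documents do not support either reading. The dominance of one group is shown for time at risk; for event rates it depends on d and r, which are unknown.

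A reader might also take safety by dosing condition to be a stated objective. It is not: the secondary objective is the safety and tolerability of oral edaravone. The by-condition tables are descriptive, and no test or within-subject contrast of adverse events is planned.

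Other points have weight. Adverse drug reactions are tabulated separately and all events are listed, and the relatedness judgement considers timing. Ascertainment is probably not constant, since no visit is scheduled between discharge and readmission. Period V is not randomised and comes last for everyone, so it is confounded with time under any window.

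A hard 48-hour cut would also be wrong. Two conditions (C and F) have their last assessment at 46 hours, the 48-hour sample may fall at 47–50 hours (SAP 7.2), and onset time is recorded only in hospital. Laboratory events take the test date as onset, and tests on Day X and at end of study come later still. In MT-1186-J02, 3 of the 7 related events were ALT or AST increases, so such events must not lose their condition.

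Against this, background events are likely to matter: of 21 + 27 events in the two earlier oral studies, only 1 + 7 were judged related, leaving 40 of 48. (The first study included 20 subjects on placebo.)

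**Conclusion.** The concern holds in a limited form. The windows are unequal and the percentages are unadjusted. Among A–D the effect is noise: about 73% of each condition's 88–92 subject-days belongs to one group of four, a different group each time. The only systematic imbalance is Period V against A–D. It amounts to about 1.2–1.4 times the expected count of subjects with an event at a 7-day follow-up, and 0.9–1.7 over the visit window, so even its direction depends on visit timing. These ratios assume a constant background rate of 0.005–0.04 per subject-day and no true difference. The Day 23/Day 24 conflict needs no assumption: under the visits in SAP 9.3, no administration falls on Day 23 to close the Period IV window or open the Period V window. This is a minor-to-moderate point on a descriptive secondary output; the food-effect analysis is untouched.

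**What to change.** In SAP 7.1.2.1(5) and the by-condition tables of 8.3.1, split each condition's events in two:

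- (a) Onset from dosing to the earlier of the next dose or the scheduled 46/48-hour assessment, inclusive. This is the like-for-like comparison in window length for all five conditions. Ending at the assessment keeps discharge findings with their condition.
- (b) Later onset, shown separately with the last condition received still identified. Delayed events, including laboratory events found on Day X or at end of study, then stay attributed. Events starting after discharge, where no onset time is collected, go here.

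Add a footnote that Period V is non-randomised and last, so column (a) aligns its window but not its timing.

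Reconcile the Period V dose day between SAP 7.1.2.1(5) and 9.3, and restate the Period IV and V windows accordingly.

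The cost is SAP wording and one derived variable. No new data are needed, because onset times are already recorded in hospital (Protocol 9.2.5.2), and no event is dropped. The small downside is an extra column and fewer events in the like-for-like columns.

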In terms of PK, after a single dose of edaravone solution or suspension in the fasting state, plasma concentrations reached C_{max} 0.3 to 0.4 hours and 0.4 to 0.8 hours after dose, respectively. Subsequently they were excreted in 2 and 3 phases, and $t_{1/2}$ of the terminal phase were 2.4 to 3.2 hours and 5.1 to 11.8 hours, respectively. C_{max} and AUC of edaravone increased more than dose proportional manner over a dose range of 30 to 300 mg. Plasma concentrations of sulfate conjugate and glucuronide conjugate, both are edaravone metabolites, reached C_{max} 0.5 to 1.4 hours and 0.5 to 1.1 hours after dose, respectively. They were excreted from plasma, with $t_{1/2}$ of 4.9 to 7.9 hours and 2.8 to 5.9 hours, respectively. Meal-effect examination after administration of 200 mg suspension (200 mg/10 mL 0.1% polyvinyl alcohol solution) showed that when edaravone was administered 30 minutes after a meal, C_{max} and AUC of plasma edaravone decreased to 18.2% and 39.1% of those when it was administered in the fasting state, respectively. Comparison between plasma concentrations in Caucasian subjects and those in Japanese subjects after administration of 200 mg suspension (200 mg/10 mL) showed that C_{max} and AUC of plasma edaravone in Caucasian subjects were 75% and 79% of those in Japanese subjects, respectively. Five-day multiple doses resulted in no accumulation

Confidential

in plasma concentrations of edaravone.

In a clinical pharmacology study of oral edaravone in healthy adult male subjects (as a drug interaction study and as a preliminary study on dosage and administration) (MT-1186-J02 study), edaravone oral suspension was orally administered to 84 subjects. Drug interaction, safety, and tolerability of 120 mg edaravone oral suspension were investigated in 66 subjects; and PK, effects of race or meal, safety, and tolerability of 100 mg were investigated in 18 subjects.

In terms of safety, no serious adverse events occurred. A total of 27 adverse events were observed in 84 subjects. Among them, 7 adverse events (diarrhoea 4, ALT increased 2, and AST increased 1) were assessed as causally related to the administration. All of them were mild in severity and rapidly resolved. No adverse events led to discontinuation in any subject.

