9.2.5.1 Objective findings

The investigator (or subinvestigator) will check for results of all of the following tests without delay.

Confidential

The investigator (or subinvestigator) or study collaborator will record the dates and times of measurement and blood/urine sampling in the CRF.

(1) General laboratory tests

The following test items will be measured. The approximate blood volume per sampling is approximately 2 mL for the following 1), 6 mL for 2), 1.8 mL for 3), and 6 mL for 5), described below. The investigator (or subinvestigator) or study collaborator will provide the sponsor with electronic data on the measurement results (except for the result of coagulation test and hCG) of the subjects who received the investigational product. Blood will be collected in the fasting state.

1) Hematology:

Hemoglobin, hematocrit, red blood cell count, white blood cell count, platelet count, MCH, MCHC, MCV, differential white blood count

2) Biochemistry:

Na, K, Cl, Ca, inorganic phosphorus, urea nitrogen, creatinine, uric acid, total bilirubin, direct bilirubin, ALT, AST, γ -GTP, ALP, LDH, CK, amylase, total cholesterol, triglycerides, LDL-C, HDL-C, total protein, albumin, glucose

3) Coagulation test:

Prothrombin time, activated partial thromboplastin time

4) Urinalysis (qualitative test):

Sediment, qualitative tests (pH, specific gravity, protein, glucose, occult blood, urobilinogen, bilirubin, ketones)

hCG (performed only for female subjects at screening, on Day -1 (hospitalization), and at the end-of-study assessment)

Time points: To be performed in the fasting state at the following time point (before breakfast).

Screening	No specifications
Day -1 (hospitalization)	No specifications
Day 5	Pre-dose
Day 9 (discharge)	Before breakfast
Day X ^{a)} (hospitalization)	No specifications
Day X+3 ^{a)} (discharge)	Before breakfast
End-of-study assessment or withdrawal assessment	No specifications

a) X = Day of hospital admission in period V

Frequency of blood sampling: 7

Total blood sampling volume: 74.6 mL (for details, see "9.3 Blood Sampling Volume")

(2) Vital signs (blood pressure, pulse rate, body temperature)

Systolic and diastolic blood pressure, pulse rate, and axillary body temperature (in Celsius; rounded to one decimal place) of each subject will be measured at the time points shown in the table below. The investigator (or subinvestigator) or study collaborator will record the date, time, and results of the measurement in the CRF.

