9.2.5.2 Adverse events

An adverse event (AE) is any untoward medical occurrence or unintended sign (including an abnormal laboratory finding), symptoms, and disease in a patient or subject who is administered a pharmaceutical product during safety assessment period, and which does not necessarily need to have a causal relationship with the treatment.

The investigator (or subinvestigator) will assess AEs that occur in the subjects from the start of investigational product administration to the end-of-study assessment and record the results in the CRF.

(1) Symptoms and diseases

The investigator (or subinvestigator) will assess whether any AE has occurred in the subjects based on the interview and physical examination.

(2) Objective findings

The investigator (or subinvestigator) will identify any clinically significant abnormal finding* and handle it as an AE.

* “Clinically significant abnormal findings” will be identified according to the following criteria.

- If a clinical sign or symptom is related to the abnormal findings.
If these symptoms or signs are reported as AEs, the related abnormal laboratory findings will not be reported as separate AEs.
- If any internal or surgical treatment is given to the subject for the laboratory abnormality.

Confidential

- If the investigational product dosing regimen is changed due to the laboratory abnormality (e.g., dose change, or an interruption or discontinuation of the investigational product).
- If the investigator (or subinvestigator) judges the abnormality as clinically significant for other reason(s).

(3) Assessments and criteria of AEs

1) Date of onset

The date of onset is defined as the date when symptoms are detected or the date when a laboratory test is performed for laboratory abnormalities. In this study, the onset time will also be recorded for all AEs occurring during hospitalization.

2) Severity

The severity of AEs will be classified as shown below.

- (1) Mild: The event does not interfere with activities of daily living.
- (2) Moderate: The event interferes to some extent with activities of daily living.
- (3) Severe: The event interferes significantly with activities of daily living.

3) Seriousness

The seriousness of AEs will be classified as shown below.

1. Not serious: AEs not meeting the criteria listed in 2.
2. Serious: A serious AE (SAE) meets any of the following, from a) to g).

- a) Death
- b) A case which may lead to death

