13.4.3 Safety

(1) Adverse events and adverse drug reactions

Adverse events will be coded according to MedDRA (version 21.0 or higher). The number and proportion of subjects with adverse events and adverse drug reactions will be calculated by dosing condition.

(2) Vital signs and laboratory tests

For vital signs (systolic and diastolic blood pressure, pulse rate, and body temperature) and laboratory data (hematology, biochemistry, coagulation test, and urinalysis), descriptive statistics will be calculated for the values at each time point and the changes from baseline by dosing condition. The values of urinalysis will be presented in a shift table by dosing condition.

(3) 12-lead ECG

For 12-lead ECG, descriptive statistics of the values at each time point and the changes from baseline will be calculated by dosing condition.

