8.3.2. Laboratory Tests

Absolute values and changes from baseline, except for urinalysis will be summarized descriptively by group and scheduled visit.

For urinalysis, number and percentage will be presented. Shift tables will present the changes in clinically relevant categories from baseline to each scheduled post-baseline visit by group and scheduled visit.

Below is a list of the laboratory test.

Laboratory Test	Parameters
Hematology	Hemoglobin, hematocrit, red blood cell count, white blood cell count, platelet count, MCH, MCHC, MCV, differential white blood count
Biochemistry	Na, K, Cl, Ca, inorganic phosphorus, urea nitrogen, creatinine, uric acid, total bilirubin, direct bilirubin, ALT, AST, γ -GTP, ALP, LDH, CK, amylase, total cholesterol, triglycerides, LDL-C, HDL-C, total protein, albumin, glucose
Coagulation test	Prothrombin time, activated partial thromboplastin time
Urinalysis	Qualitative tests (pH, specific gravity, protein, glucose, occult blood, urobilinogen, bilirubin, ketones), sediment(listing only)

All data including clinically relevant flagged will be listed. Any BLQ data will be treated as 0 in summary statistics.

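### Scheduled laboratory tests cannot place a laboratory adverse event under a Period I or III meal condition, so the by-condition adverse event counts for Periods I-IV are not interpretable for that class of event

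*SAP*

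**What the plan says.** Protocol 9.2.5.2 sets the onset of a laboratory AE as "the date when a laboratory test is performed for laboratory abnormalities". It adds that "the onset time will also be recorded for all AEs occurring during hospitalization", so a finding from the Day 5 pre-dose sample falls before the Day 5 dose.

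Protocol 9.2.5.1(1) schedules seven safety laboratory samplings: screening, Day -1, Day 5 pre-dose, Day 9, Day X (admission for Period V), Day X+3 and end of study. SAP 9.3 shows the same pattern.

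SAP 7.1.2.1(5) gives each AE to the dosing window that contains its onset. The Period II window is "From on or after administration date/time in Day 3 to before administration date/time on in day 5"; the Period IV window is "From on or after administration date/time in Day 7 to before administration date/time on in day 23".

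Protocol 13.4.3 says "The number and proportion of subjects with adverse events and adverse drug reactions will be calculated by dosing condition", and SAP 8.3.1 produces the AE tables by treatment. Laboratory values are handled differently: under SAP 8.3.2, "Absolute values and changes from baseline, except for urinalysis will be summarized descriptively by group and scheduled visit". SAP 7.2 likewise gives laboratory tests one baseline before the first dose, where other safety parameters have a baseline in each period.

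**The concern.** The rule gives laboratory AEs a single meal condition that the sampling schedule cannot support. Each of the two samples taken during the first admission (Day 5 pre-dose and Day 9) follows two doses under two different conditions, and the finding is credited wholly to the second. SAP 8.3.2 already avoids this for laboratory values by not summarising them by meal condition, but the AE tables carry no matching rule or caveat.

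Safety is part of the secondary objective, and this kind of event is plausible. Protocol section 1(3)2) reports that in study MT-1186-J02 "7 adverse events (diarrhoea 4, ALT increased 2, and AST increased 1) were assessed as causally related to the administration". Exposure is also expected to differ by condition: dosing 4 hours after a meal reduced Cmax to 55.9% and AUC to 75.7% of fasted values in the earlier work (Protocol 8.3). A reader may therefore compare the fasted column with the meal columns, and for laboratory AEs that comparison mixes neighbouring conditions.

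**Working it through.** **1. The schedule.** Two samplings before the first dose plus five after it give 7, as stated. The volume also reproduces: 6×1 + 2×7 + 6×7 + 1.8×7 = 74.6 mL.

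**2. Scheduled post-dose tests placed in the SAP 7.1.2.1(5) windows.**

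| Window | Scheduled laboratory tests | Condition in Groups 1 / 2 / 3 / 4 |
|---|---|---|
| Period I | none | A / B / C / D |
| Period II | Day 5 pre-dose | B / C / D / A |
| Period III | none | C / D / A / B |
| Period IV | Day 9, Day X | D / A / B / C |
| Period V | Day X+3, end of study | same condition in all groups |

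SAP 7.1.2.1(5) places the Period V dose on Day 23, while SAP 9.3 lists the Period V pre-dose assessment on Day 24. The mapping is the same either way, because Day X is the admission day before that dose.

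**3. Subjects without a test.** Each of A-D falls in Period I or III for two groups of 4, so 8 of 16 subjects have no scheduled test in that condition's window. For Period V it is 0 of 16. Scheduled samplings per condition are 4×1 + 4×2 = 12 for each of A-D, against 16×2 = 32 for Period V.

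**4. Direction of movement.** The sequences are cyclic, so the condition following a Period I or III dose is always the same: A to B, B to C, C to D, D to A, 8 subjects each.

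**5. Effect on the tables.** Let p be the chance that one dose causes a laboratory AE. Assume that p is small, that every such AE persists to the next scheduled test, and that second-dose effects are visible at that test. The tabulated rate for a condition is (8×p_own + 8×p_preceding)/16:

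- A: (pA + pD)/2
- B: (pB + pA)/2
- C: (pC + pB)/2
- D: (pD + pC)/2

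The contrasts with fasted are then:

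- A − B = (pD − pB)/2
- A − C = (pA + pD − pB − pC)/2
- A − D = (pA − pC)/2

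Illustration with assumed values pA = 10% and the others 2%: A 6%, B 6%, C 2%, D 2%. The true A − B of 8 points is tabulated as 0, and the true A − D of 8 points as 4.

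**6. Expected counts.** The documents give no per-dose rate, so it is assumed. The expected count per condition is 16p, of which 8p would appear under the next condition.

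| Assumed p | Events per condition | Shown under the next condition |
|---|---|---|
| 2% | 0.32 | 0.16 |
| 3/84 = 3.6% | 0.57 | 0.29 |
| 5% | 0.80 | 0.40 |
| 10% | 1.6 | 0.8 |

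The 3/84 row treats the three ALT/AST events in J02 as one per subject and the per-subject rate as a per-dose rate.

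**The case against.** A reader might infer that half of the fasted condition's laboratory AEs will be reported under B, and that the fasted effect vanishes from the tables. The documents do not support either as a general statement. Movement requires the abnormality to last until the next scheduled test; one that resolves sooner is missed rather than moved. The complete cancellation applies only to A − B: A − C and A − D both retain pA. The SAP plans counts and percentages, not a formal contrast of AEs between conditions, and the shift is symmetric across A-D, each giving 8 subjects and receiving 8.

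The expected number of events is also low. In study MT-1186-J01, 54 subjects received edaravone at doses up to 300 mg, and the only related AE was one headache. Pooling the two oral studies gives 3/(54 + 84) = 3/138 = 2.2% per subject, if the three events were in different subjects. Read as a per-dose rate, that is about 0.35 events per condition, with about 0.17 moved. The documents do not say which J02 subjects had the events, and 66 of the 84 were in a drug-interaction investigation.

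There is mitigation too. Only clinically significant findings become AEs, findings belonging to a reported symptom AE are not reported separately, and all AEs and laboratory data are listed, so individual events can be traced.

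These points limit the size of the problem. They do not change the mapping: no scheduled test falls in the Period I or III window, and the tables will still print a single condition for findings that follow two. In tables this sparse, one misplaced event is visible.

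**Conclusion.** The point holds as a limit on attribution. For AEs found by scheduled laboratory tests in Periods I-IV, the by-condition counts do not identify the dose responsible. A Period I or III condition can never receive such an event, and half of the subjects in each A-D denominator (8 of 16) could not contribute one. This follows directly from the onset rule, the test schedule and the windows, and needs no assumption about rates. The size of any distortion does rest on assumptions: with full persistence and 2% to 10% per dose, 0.16 to 0.8 events per condition would appear under the next one.

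The scope is narrow. Symptom AEs take the symptom date, and ECG and vital signs are measured in every period. Unscheduled tests inside Period I or III fall in their own window. Period V tests follow a single new dose after a Day X sample. Pharmacokinetic blood is drawn in every period, and the food-effect analysis is untouched. The change is worth making because it is cheap and brings the AE tables into line with SAP 8.3.2.

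**What to change.** - In SAP 7.1.2.1(5) and 8.3.1, tabulate AEs identified by a scheduled laboratory test in Periods I-IV by group and sampling interval (Periods I-II, Periods III-IV). Define the class by how the AE was identified, so that symptom AEs that happen to start on a test date stay in the by-condition tables.
- Keep these events in the overall AE total, with a footnote that they are not attributable to one dosing condition.
- Leave laboratory AEs from Day X+3 and end of study under the Period V condition.
- Record the change, with its reason, in SAP section 10 as a departure from Protocol 13.4.3. That section currently states that there are none.
- Reconcile the Period V dosing day between SAP 7.1.2.1(5) (Day 23) and SAP 9.3 (Day 24).

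The cost is SAP wording, one small table and the section 10 entry; no new data are needed. The downside is that laboratory AEs from Periods I-IV no longer have a per-condition figure.
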